11.2.4.3 WATER SUBMERSION BATH TEST

Prior to starting the Water Immersion Bath Test, the subject’s blood pressure is to be taken and recorded on the CPM response form. After this, the subject will be asked to submerge their arm (the opposite one from the one used for the Thermode tests) into a bath of 12 degree water. The Research Assistant will verbally ask the subject to rate their pain every 15 seconds on a scale from “0” being no pain to “10” worst pain tolerable. The subject’s blood pressure will be taken and

again after 1 minute of submersion. Their responses and the blood pressure readings should be indicated on the CPM response form.

11.2.4.4 THERMODE TEST AFTER BATH

For the Thermode test, the subject's "Left Forearm Medial" will be used. Select the site just below the site used for the previous test.

This Thermode Test is for another duration of 2 minutes and the temperature remains at the subject's VAS50% temperature throughout. Although the temperature remains constant at the subject's VAS50%, the subject is instructed that the temperature will vary throughout the test. The subject should indicate their pain intensity with the CoVAS device with "0" being no pain at all and "10" being the worst pain tolerable. If the Research Assistant feels there was an issue with the test, repeat the test.

The pain threshold and the pain tolerance should be recorded on the CPM response form.

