11.2.3.2.1 UNPLEASANT FACTOR OF PAIN

The Research Assistant will describe various experiences or sensations the subject will feel throughout the test. The subject needs to understand the temperature will continue to increase – going from warm to hot, then to a point they will feel pain, and eventually to the point it will be too painful at which point they should stop the test. The subject should be instructed to indicate – “warm” as they feel the increase in temperature; “pain” due to the heat, and “stop” when it is too painful.

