11.2.4.1 QST THERMAL VAS50% DETERMINATION PRE-TEST

Once the patient understands, move to New Test and change the body site to “Forearm Medial” and save the changes. The forearm “pre-test” is used to determine the temperature corresponding to the patient’s VAS50%. The pain and threshold tolerance temperatures are also noted.

- Place the Thermode on the subject’s forearm approximately 1 inch below the crook of their elbow. Start the pre-test. The subject should indicate three things to the Research Assistant – that the Thermode is “warm”, that it’s “hot” and finally “stop” when it is too painful to continue. The subject will rate their pain intensity with the CoVAS throughout the test. If the subject seems to not understand the test, or the Research Assistant feels there was an issue with the test, repeat the test.

Once the Thermode Pre-Test is successfully completed, proceed to the Thermode Test.

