11.2.4.2 THERMODE TEST BEFORE BATH

The Research Assistant will prepare the Software for the Thermode Test. The subject’s VAS50% score will be used to personalize the Thermode Test.

1. For the Thermode test, the subject’s “Left Forearm Medial” will be used. Select the site just below the site used for the pre-test.
2. This Thermode Test is for a duration of 2 minutes and the temperature remains at the subject’s VAS50% temperature throughout. Although the temperature remains constant at the subject’s VAS50%, the subject is instructed that the temperature will vary throughout the test. The subject should indicate their pain intensity with the COVAS device with “0” being no pain at all and “20” being the worst pain imaginable. Assistant feels there was an issue with the test, repeat the test.
3. The pain threshold, VAS50% and the pain tolerance should be recorded on the CPM response form.

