14.5 SOURCE DOCUMENTATION

The following outcome measures will be used to collect data and will be considered source documents:

The above questionnaires are all considered source documents in addition to the following:

- ✓ The Faces Pain Scale – Revised (FPS-R)
- ✓ State-Trait Anxiety Inventory - (STAI-C)
- ✓ Pain Catastrophizing Scale (PCS)
- ✓ Functional Disability Index (FDI)
- ✓ Revised Children Anxiety and Depression Scale (RCADS)
- ✓ Pittsburgh Sleep Quality Index (PSQI)
- ✓ Neuropathic Pain Questionnaire (DN4)
- ✓ Tampa Scale for Kinesiophobia (TSK)
- ✓ Scoliosis Research Society Questionnaire- Quality of Life Tool (SRS-30)
- ✓ The Adolescent Pediatric Pain Tool (APPT)
- ✓ Patient's Global Impression (PGIC)
- ✓ Blood Sample Collection Form
- ✓ MDT/PPT Data Collection Form

- ✓ CPM Data Collection Form
- ✓ Surgical Data Collection Form
- ✓ Concomitant Medication Form
- ✓ AE & SAE Form
- ✓ Spinal Deformity Intra-Operative Monitoring Work Sheet (SDIM)
- ✓ Patient Home Interview / Phone Call Form

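### The recording lines for the CPM heat runs ask for pain threshold and tolerance, which a constant-temperature run cannot yield, and omit the CoVAS rating from which CPM is derived

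*Combined protocol and SAP*

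**What the plan says.** Section 11.2.4 runs the thermal test in sequence: a palm familiarization, a forearm pre-test, a thermode run, a cold-water bath for the other arm, and a second thermode run.

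The forearm pre-test (11.2.4.1) finds the temperature that matches the patient's VAS50%. It adds: "The pain and threshold tolerance temperatures are also noted". The two CPM runs then use that one temperature. Before the bath (11.2.4.2): "This Thermode Test is for a duration of 2 minutes and the temperature remains at the subject’s VAS50% temperature throughout". After the bath (11.2.4.4): "This Thermode Test is for another duration of 2 minutes and the temperature remains at the subject's VAS50% temperature throughout". In both runs the patient rates pain on the CoVAS.

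The recording instruction before the bath is: "The pain threshold, VAS50% and the pain tolerance should be recorded on the CPM response form". After the bath it is: "The pain threshold and the pain tolerance should be recorded on the CPM response form".

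Section 14.3 says that source data are collected on paper forms, and section 14.5 lists the "CPM Data Collection Form" among the source documents. I take this to be the form that section 11.2.4 calls the CPM response form.

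On the verbal cues, section 11.2.3.2.1 tells the patient what to expect as the heat rises: "going from warm to hot, then to a point they will feel pain, and eventually to the point it will be too painful". There and in the palm pre-test (11.2.4) the middle cue is 'pain' or 'painful'. In the forearm pre-test (11.2.4.1) it is 'hot'.

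**The concern.** The two recording lines appear to ask for the wrong quantities. Threshold and tolerance are points reached on a rising temperature, and the CPM runs do not rise. What the runs do produce is a pain rating at a fixed stimulus, and neither line mentions it.

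CPM is not a side measurement here. Sections 8.1 and 9.1 use the baseline result to split patients into two strata before randomization, and both comparisons listed in section 16.5 are defined by that split. CPM is tested again on Day 5, at 6 weeks and at 6 months, where it serves the mechanistic objective in section 6. If the form is completed exactly as the protocol says, the number that decides the stratum is not on it, and staff have no rule for reducing a 2-minute trace to one value.

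The forearm cue is a smaller matter of the same kind. A threshold taken when the patient says 'hot' would come before pain begins.

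**Working it through.** The plan gives no figure on this point to reproduce, so the check is mainly a comparison of texts.

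| Step | Temperature | Patient's response | What is to be written down |
|---|---|---|---|
| Forearm pre-test (11.2.4.1) | Rising | Cues 'warm', 'hot', 'stop'; CoVAS throughout | VAS50% temperature; pain threshold and tolerance temperatures |
| Run before bath (11.2.4.2) | Constant at VAS50%, 2 minutes | CoVAS, described as 0–20 | Threshold, VAS50%, tolerance |
| Cold bath (11.2.4.3) | 12-degree water | Verbal rating every 15 seconds, 0–10 | The ratings and blood pressure, on the CPM form |
| Run after bath (11.2.4.4) | Constant at VAS50%, 2 minutes | CoVAS, described as 0–10 | Threshold, tolerance |

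1. **Can the runs yield the listed items?** Section 11.2.4.1 treats threshold and tolerance as temperatures, and section 11.2.3.2.1 has them signalled as the heat increases. At one fixed temperature there is no onset temperature and no stopping temperature to read. So the runs cannot yield them.

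2. **Could the lines mean pre-test values?** Before the bath, possibly: VAS50% is in the list and is a pre-test value. After the bath, no: no new ramp comes between the two runs, so the entry would either repeat old values or have no defined origin.

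3. **What does CPM need?** Section 4 describes CPM as a reduction in pain and, for an earlier healthy-subject study, names a 10% reduction as the minimal clinical change. In this test, that corresponds to the change in CoVAS rating between the two runs. Neither recording line names the rating or a summary of it (mean, peak, time window). Section 11.2.4.3 does send the cold-bath ratings to the CPM form, so the protocol says so where a rating is to be recorded.

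4. **Is the rating captured elsewhere?** Yes. Section 11.2.3.2 connects the CoVAS to the laptop software, and section 11.2.3 has a subject file created there. Export, retention and extraction of a summary are not described.

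5. **Are the two runs on one scale?** As written, no: 0–20 before the bath and 0–10 after it. Suppose the same mid-scale sensation in both runs, with raw numbers used.
   - Before: 0.5 × 20 = 10. After: 0.5 × 10 = 5.
   - Apparent reduction: (10 − 5) / 10 = 50%.
   - As fractions of the scale: 10/20 = 0.5 and 5/10 = 0.5, so the true change is 0%.

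   Sections 11.2.3.2 and 11.2.3.2.2 introduce the CoVAS as 0–10, so the 20 may be a slip. The example shows only why the anchors must match before a change score is defined.

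6. **The forearm cue.** Section 11.2.3.2.1 places hot before pain. A threshold taken at the 'hot' cue therefore precedes pain. VAS50% is a point on the pain-rating scale, which the patient gives on the CoVAS throughout the pre-test, so the verbal cue changes neither VAS50% nor the stratum.

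**The case against.** The strongest reply is that nothing is lost. Pain is rated in both runs and the slider feeds the software. The form itself is not in the documents, and neither line says that its items are the only fields. The line in 11.2.4.2 reads naturally as carrying pre-test values onto the form, and the line in 11.2.4.4 may be a copy of it. Section 14.5 also omits other forms that the protocol uses, such as the Anesthesia Data Collection and Sedation Level forms, so the absence of a CoVAS export from that list proves little. All of this stands, and it limits the point to what the protocol instructs and what the source form is told to hold. It does not rescue 11.2.4.4, and it does not supply the missing summary.

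Three stronger readings are tempting, and the documents do not support them.

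- *That the strata cannot be verified at all.* The software holds the ratings. What is missing is an instruction on which summary to extract and where to record it.
- *That patients are misclassified.* A gap in a recording line does not by itself move anyone between strata, and the documents show no case where it would.
- *That the 'hot' cue biases a planned result.* Patients have already been told to say 'pain' and have practised 'painful' on the palm. A pain onset could also be read from the CoVAS trace, although the text does not say so. No endpoint or analysis in section 16 names the forearm heat-pain threshold, and the palm test is only for familiarization.

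**Conclusion.** The point holds in a limited form. The recording line in 11.2.4.4, and on its plain reading the one in 11.2.4.2, asks for quantities that a constant-temperature run cannot give and leaves out the rating on which CPM rests. The defect is one of specification and traceability in the stratifying variable. It is not a loss of data.

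Its reach is the baseline CPM test of all 150 planned patients, plus up to three later tests each. That counts the tests covered by the instruction; it does not count errors. The size of any effect on classification cannot be worked out, because the plan gives no CPM formula or cut-off for this trial; the 10% in section 4 belongs to an earlier study.

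The conclusion assumes that the CPM response form follows the protocol text and that CPM is calculated from the CoVAS ratings in the two runs. If the form already has a field for a defined CoVAS summary, the remaining fault is wording only.

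The forearm cue is a real inconsistency, but it affects only the forearm heat-pain threshold. The size of that effect is the temperature gap between 'hot' and 'pain', which the documents do not give.

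**What to change.** - In 11.2.4.2 step 3 and 11.2.4.4, replace the recording lines with one pre-specified CoVAS summary per run, entered on the CPM form. The mean over the same time window in each run is one reasonable choice; any fixed summary would do.
- Define CPM as the before-to-after change in that summary.
- Use identical CoVAS anchors, in number and in wording, in both runs. Do this first, since a percent change is meaningless across 0–20 and 0–10.
- Keep threshold, VAS50% and tolerance as pre-test items, recorded once under 11.2.4.1.
- Retain the CoVAS software export as source and add it to section 14.5, so that the form entry can be checked against it.
- In 11.2.4.1, align the middle cue with the 'pain' or 'painful' cue in 11.2.3.2.1 and 11.2.4.

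The cost is protocol wording and one revised form. No new measurement is needed, because the software already takes the ratings. For patients already tested, the chosen summary could be extracted from the stored traces if these were kept.

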12 PAIN ASSESSMENT QUESTIONNAIRES

The following questionnaires used for this study:

- ✓ The Faces Pain Scale – Revised (FPS-R) [61-63]
- ✓ State-Trait Anxiety Inventory - (STAI-C) [64]
- ✓ Pain Catastrophizing Scale (PCS) [65]
- ✓ Functional Disability Index (FDI): measures physical functioning in school age children and adolescents. This measure asks about being able to do a range of everyday physical activities (Walker and Greene 1991).
- ✓ Revised Children Anxiety and Depression Scale (RCADS): is a 47-item scale intended to assess children's report of symptoms corresponding to selected DSM-IV anxiety disorders and depression (Chorpita, Yim et al. 2000).
- ✓ Pittsburgh Sleep Quality Index (PSQI): designed to assess different clinically derived domains of sleep difficulties (Buysse, Reynolds et al. 1989).
- ✓ Neuropathic Pain Questionnaire (DN4): consists of both sensory descriptors and signs related to bedside sensory examination (Bouhassira, Attal et al. 2005).
- ✓ Tampa Scale for Kinesiophobia (TSK) [70]
- ✓ Scoliosis Research Society Questionnaire- Quality of Life Tool (SRS-30) [71]
- ✓ The Adolescent Pediatric Pain Tool (APPT): measures the location, intensity and quality of pain (Savedra, Holzemer et al. 1993).
- ✓ Patient's Global Impression (PGIC)

12.1 IN-HOSPITAL ADDITIONAL MEASURES:

As analgesics may influence reported pain score, as may the anesthetic during the surgery, all perioperative medication intake will be recorded. Patient's medical charts will be reviewed to document patients demographics. Vital signs will be recorded on admission, measured throughout the surgical procedure as well as during the post-operative period. To minimize variability our care plan has been standardized and implemented over the last 3 years. No changes to standard care will be required as a result of participation in this study on the day of surgery. In the operating room, general anesthesia and pharmacological pain management will be induced and maintained in a manner consistent with the standard of care standardized perioperative protocol established and respected by the anesthesiologists collaborating in this study. Following the surgical procedure, postoperative pain management is controlled in a standardized fashion by the Acute Pain Service (APS). As per standard care, the patient's pain is monitored continuously and as needed the APS adjusts the level of narcotics given. Tracking of self-reported pain scores and all analgesics given are reported in the patient's charts and accessible to the research team. A mean of all numerical pain scores for the first 48 hours after surgery will be calculated. The cumulative intake (mg/kg/hr) of each analgesic agent will be calculated for the first 48 hours after surgery as well.

Patients x-rays will be reviewed and spinal deformity will be quantified using standard Cobb angle measurements and using EOS technology will have 3D rendering of their spinal deformity.

Patient's radiographic imaging will be used to generate individual anatomical spinal profiling. 3D imaging using EOS technology will be used to define patient's spinal deformity. Each 3D rendition will be analyzed for: identification of the plane of maximal deformity in 3D using 3D vectors; identification of relative change from one segmental deformity to the adjacent segmental deformity across the entire spine; defining the plane of maximal correction and its impact on the other segmental deformities of the spine. In addition, relative findings of spinal imbalance will also be correlated to the presence or absence of pain which may influence overall spinal balance. Subsequently, patients with postoperative loss of normal sagittal alignment will be identified. Each case will then be illustrated on a DaVinci Diagram (axial 3D representation of the spinal deformity) providing clues as to why these individual patients have aberrant spinal alignment and possible postoperative spinal imbalance. 3D rendition will also be used to generate finite element models estimating anatomical forces across the intervertebral discs and the facets.

12.1 STUDY PLAN TABLE

	Baseline	Surgery	In-Hos Day 1	In-Hos Day 2	In-Hos Day 3	In-Hos Day 4	In-Hos Day 5	Patient Diary call	6 week	6 month
Blood Sample	X	X	X	X			X		X	X
Randomization	X (After QST results obtained)									
Clonidine or Placebo Intrathecal/Spinal		X								

Clonidine or Placebo PO			X	X	X	X	X			
dnadPaQST- Mechanical (MDT)	X	X	X	X			X		X	X
QST – Pressure Pain Threshold (PPT)	X	X	X	X			X			
QST-CPM	X						X	X	X	X
Questionnaires	X	X	X	X	X	X	X	X	X	X
X-rays	X	X	X	X	X	X	X		X	X
Medication	X	X	X	X	X	X	X		X	X
Vital signs	X	X	X	X	X	X	X		X	X

13. SUBJECT SAFETY

13.1 SAFETY AND TOXICITY ASSESSMENT

The experimental procedures in this study are the additional blood test, the QST testing and the use of Intrathecal Clonidine.

During the blood test the patient may suffer malaise, slight bleeding and/or minor bruising at the blood draw site.

In terms of QST, the patient may suffer some mild discomfort and reddening of the test site. The thermode will shut off after 50°C so there is no risk to burn the patient. The patient is always in control of their pain level and can stop the test at any time.

There are potential risks to patients the use of Clonidine. These are listed in section 5.2. Patients are followed for 6 months in this study and will be assessed for AEs at each follow up visit.

Additional risks associated with the study are in relation to confidentiality and data collection.

The benefit of using Intrathecal Clonidine is that patients may suffer less pain during the peri-operative period.

13.2 ADVERSE EVENT AND ADVERSE DRUG REACTION (ADR)

Any untoward medical occurrence in a patient or clinical investigation subject administered a pharmaceutical product and which does not necessarily have a causal relationship with this treatment.

All noxious and unintended responses to a medicinal product related to any dose should be considered adverse drug reaction.

13.3 SERIOUS ADVERSE EVENT OR ADVERSE DRUG REACTION

A serious adverse drug reaction (experience) or reaction is any untoward medical occurrence that at any dose:

- Results in death
- Is life-threatening
- NOTE: The term "life-threatening" in the definition of "serious" refers to an event in which the patient was at risk of death at the time of the event; it does not refer to an event which hypothetically might have caused death if it were more severe.
- Requires inpatient hospitalization or prolongation of existing hospitalization
- Results in persistent or significant disability/incapacity, or
- Is a congenital anomaly/birth defect.

Medical and scientific judgment should be exercised in deciding whether expedited reporting is appropriate in other situations, such as important medical events that may not be immediately life-threatening or result in death or hospitalization but may jeopardize the patient or may require intervention to prevent one of the other outcomes listed in the definition above. These should also usually be considered serious.

13.4 ANTICIPATED ADVERSE DRUG REACTIONS

An anticipated AE is any event, which is described below and can be clearly connected to one of the treatments. It is consistent with the specificity or severity and/or the risk information described in the product monographs for Clonidine Hydrochloride injection, and for Clonidine Hydrochloride Tablets.

Endocrine disorders:

≥0.01% and <0.1% gynaecomastia

Psychiatric disorders:

≥1% and <10% depression, sleep disorder

≥0.1% and <1% delusional perception, hallucination, nightmare

Not known confusional state, libido decreased

Nervous system disorders:

≥10% dizziness, sedation

≥1% and <10% headache

≥0.1% and <1% paraesthesia

Eye disorder:

≥0.01% and <0.1% lacrimation decreased

Not known accommodation disorder

Cardiac disorders:

≥0.1% and <1% sinus bradycardia

≥0.01% and <0.1% atrioventricular block

Not known bradyarrhythmia

Vascular disorders:

≥10% orthostatic hypotension

≥0.1% and <1% Raynaud's phenomenon

Respiratory, thoracic and mediastinal disorders:

≥0.01% and <0.1% nasal dryness

Gastrointestinal disorders:

≥10% dry mouth

≥1% and <10% constipation, nausea, salivary gland pain, vomiting

≥0.01% and <0.1% colonic pseudo-obstruction

Skin and subcutaneous tissue disorders:

≥0.1% and <1% pruritus, rash, urticaria

≥0.01% and <0.1% alopecia

Reproductive system and breast disorders:

≥1% and <10% erectile dysfunction

General disorders and administration site conditions:

≥1% and <10% fatigue

≥0.1% and <1% malaise

Investigations:

≥0.01% and <0.1% blood glucose increased

Most adverse effects are mild and tend to diminish with continued therapy.

Occasional reports of abnormal liver function tests and cases of hepatitis have also been reported.

13.5 SERIOUS ADVERSE EVENT AND ADVERSE DRUG REACTION REPORTING

All adverse events and all adverse drug reactions (ADRs) that are both serious and unexpected are subject to expedited reporting. As soon as study staff become aware of an ADR, it is this person's responsibility to notify the PI. The PI will ensure that SHC Headquarters and all applicable regulatory organizations are notified per regulatory guidelines.

Shriners Hospitals for Children must be notified of any unexpected ADR, via the OnCore reporting mechanism, within 10 days of occurrence.

The study PI will notify all participating investigators of any adverse drug reaction associated with the use of the drug that is both serious and unexpected, as well as any finding from tests in laboratory animals that suggest a significant risk for human subjects.

Documentation of serious adverse drug reactions requires the investigator to collect the following data in order to report to the sponsors and IRB; Subject's demographics, date event occurred, description of the event and how serious and severe it was, and whether or not it was related to the study treatment. If not related to the study treatment, what the possible causes may have been, if there is any relevant past medical history, if any tests were carried out and the results, if any concomitant medications were taken.

All data is to be documented on the AE/ADR form and filed in the patient's medical record and study file. All follow up information surrounding the event will also be documented and sent to the sponsor and IRB.

All adverse events and all adverse drug reactions will be followed up until resolved, or until the end of the patient's study participation.

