9.3.2 PLACEBO-RANDOMIZED GROUP

On Post-operative Day 1 through Day 5, both the CPM optimal and sub-optimal subjects who were randomized to the Placebo group will be instructed to take the placebo pill three (3) times a day. Patients and treating team will be blinded to which pills they will be taking.

9.4 DISCHARGE VISIT AND AT HOME PATIENT DIARY CALL - 1X/PER X 6 WEEKS

On the day of discharge, patients are assessed for any neurological deficits. These will be recorded on the SDIM Discharge form and included in the patient's study analysis.

Patients will be contacted by phone once a week for 6 weeks (or up until their 6 week visit). They will be asked about pain levels, medication intake, activity levels and their sleeping habits for the week in question. Their interview will be recorded on Patient Home Interview / Phone Call Form.

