9.5.2 PREMATURE STUDY TERMINATION

Participation of the subject in the study may end for any of the following reasons:

- The subject/subject's representative withdraws informed consent for any reason
- Occurrence of an AE or SAE that prevents the subject from continuing in the study.
- Death
- The subject does not meet eligibility criteria / fails the screening process
- Physician discretion (e.g. Patient is non-compliant with protocol)
- The subject is lost to follow up
- The Sponsor/Investigator terminates the study

Documentation of reason(s) for subject's discontinuation in the study will be detailed and explained on a File Note and entered into the patient's study file.

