13.7 UNBLINDING PROCEDURE

An investigator whose participant experiences side effects can be un-blinded if knowledge of the participant treatment is necessary in order to deliver appropriate treatment.

Should any events occur during surgery, whereby, the surgeon or anesthesiologist feel it is necessary to unblind the treatment, a call will be placed to the hospital's pharmacist who will advise which treatment the patient is receiving and the patient will be treated medically as dictated by the event.

Should any events occur during the 5 day post-operative period, whereby it is felt that it is necessary to unblind the treatment, the patient's surgeon will be contacted and will make the final decision to unblind the treatment or not. Should the response be affirmative, a call will be

placed to the hospital's pharmacist who will advise which treatment the patient is receiving. There is no need to taper off the medication as the dosage given is very small.

If un-blinding occurs and medication is stopped immediately. No dose modifications will be made. The patient will be asked to remain in the study as we can still collect valuable information through blood samples, QST and questionnaires; however, no further medications or placebos will be given.

At the conclusion of the study, all investigators will be unblended with respect to their participant's treatments.

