16.4 STATISTICAL METHODS

Primary End Point: Average pain intensity over the past 7 days (0–10 numerical rating scale where 0 indicated “no pain” and 10 “worst possible pain”) six weeks and six months after surgery (Dworkin et al., 2005).

Secondary end points: Chronicity of postsurgical pain: Six months after surgery, CPSP will be defined in a dichotomous way (yes/no) as the presence of symptoms 6 months after surgery are reported.

Descriptive statistics (means, SD, medians, n, %) will be calculated in order to present baseline characteristics of the different comparison groups and follow-up measures. To better appreciate the evolution of pain intensity (primary endpoint) during the longitudinal follow-up (baseline to six months after surgery), linear mixed models for repeated measures will be achieved for each of the three comparison schemes described above with the inclusion of the following variables as independent variables to obtain adjusted effects: age, functional outcome score and psychological profile (STAI and PCS scores). This type of analysis is justified by its flexibility in regard to missing data caused by patients lost to follow-up [75] and the possibility to adjust for potential confounders (e.g. patients’ demographics, physical and emotional functioning, clinical characteristics such as medication use or scoliosis parameters). Continuous secondary outcomes will be compared between study groups using similar models. Categorical secondary outcomes such as the presence of chronic postsurgical pain measured 6 months after surgery will be compared between study groups using Chi-square tests. The investigator that will be in charge of the statistical analyses will be blinded to group assignment. As a secondary analysis aiming at understanding the underlying changes over time in QST, pain intensity and catecholamine concentrations will be examined using repeated measures analyses.

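### An adverse event that ends participation under section 9.5.2 need not be followed to its outcome under section 13.5, and the later pain outcomes are lost with it

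*Combined protocol and SAP*

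**What the plan says.** Five places in the combined protocol and SAP bear on this.

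- **Section 9.5.2** lists reasons why a patient's participation may end. One is "Occurrence of an AE or SAE that prevents the subject from continuing in the study"; physician discretion is another. The only action required is that the reason for "discontinuation in the study will be detailed and explained on a File Note". No exit visit, final pain score or safety contact is asked for.
- **Section 13.5** sets how long events are followed: "All adverse events and all adverse drug reactions will be followed up until resolved, or until the end of the patient's study participation".
- **Section 13.1** ties adverse-event assessment to study visits: "Patients are followed for 6 months in this study and will be assessed for AEs at each follow up visit".
- **Section 13.7**, on un-blinding, stops the study drug but keeps the patient: "The patient will be asked to remain in the study as we can still collect valuable information through blood samples, QST and questionnaires". Section 10 likewise retains patients who do not take their study medication, if they wish to stay.
- **Sections 16.1, 16.2 and 16.4** set the primary endpoint as 7-day average pain at 6 weeks and 6 months, and chronic postsurgical pain at 6 months as a secondary endpoint. Pain intensity is analysed by a linear mixed model. The presence of "chronic postsurgical pain measured 6 months after surgery will be compared between study groups using Chi-square tests".

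**The concern.** The events that remove a patient from a trial are those whose outcome matters most to its safety record. Here, leaving because of an event is itself a reason to stop following it. The trial would count the event but might not record whether it resolved. This is a study of clonidine in patients aged 10 to 21. Section 13.4 lists anticipated reactions such as depression and sleep disorder, and adds: "Occasional reports of abnormal liver function tests and cases of hepatitis have also been reported". In our judgement some of these could outlast a five-day oral course.

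The same exit also removes efficacy outcomes. The primary scores come weeks and months after dosing ends, so a patient who leaves during dosing contributes neither, although nothing about a drug reaction need stop her from giving a pain score later.

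**Working it through.** **1. Do the two rules interact as described?** Sections 9.5.2 and 13.5 both turn on the individual patient's participation. Section 9.5.2 says it may end early for an event; section 13.5 ends follow-up when it ends. Possible rescues elsewhere:

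- Section 13.1 assesses events at follow-up visits, which a departed patient does not attend.
- Section 13.6 covers expedited reporting to Health Canada of reactions that are both serious and unexpected. It does not provide for following other events to their outcome.
- Section 15.2 has monitors check medical records for the occurrence of events. It does not require outcomes to be obtained after exit.

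None restores follow-up.

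**2. What one exit loses, by timing.** Study drug is given on the day of surgery and for 5 days after. Section 9.4 adds: "Patients will be contacted by phone once a week for 6 weeks". These calls cover pain, medication, activity and sleep; adverse events are not named.

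| Exit | Later visits with event assessment | Weekly calls | Primary scores | 6-month chronic-pain status |
|---|---|---|---|---|
| Day 1 to 5 | 2 of 2 lost | 6 of 6 lost | 2 of 2 lost | lost |
| After the 6-week visit | 1 of 2 lost | none | 1 of 2 lost (6 months) | lost |

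Taking 6 months as 182 days, exit on day 1 to 5 forgoes at most 182 − 5 = 177 to 182 − 1 = 181 days of follow-up of the causal event. This is a ceiling: it is reached only if the event would have stayed unresolved throughout.

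**3. The plan's own sample size.** Inputs from section 16.3: difference 2, SD 2.0, two-sided alpha 0.05, power 90%, three measurements, correlation 1. The repeated-measures factor is (1 + (3 − 1) × 1)/3 = 1, so

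n = 2 × (1.960 + 1.282)² × (2/2)² = 21.01 with unrounded quantiles, rounded up to 22 per group, as stated.

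Enrolment is 35 per group. (Section 16.3 prints 35 × 4 as 150; it is 140. The stated 35 is used here.) The margin tolerates a loss of 1 − 22/35 = 37%.

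**4. Effect of exits.** No exit rate is given. Assume k = 1 to 4 exits in a group of 35:

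- Share: 1/35 = 2.9% to 4/35 = 11.4%.
- Power: 35 − 4 = 31 remain, against 22 required.
- Primary mean: if those who leave differ from the rest by d = 1 to 2 points (assumption), leaving them out shifts the group mean by (k/35) × d, from 1/35 × 1 = 0.03 to 4/35 × 2 = 0.23 points. That is 1.4% to 11.4% of the 2-point target. At a far higher assumed loss of 30% of one arm and d = 2, the shift would be 0.30 × 2 = 0.6 points.
- Chronic pain: with k outcomes unknown, the best-case and worst-case group rates differ by k/35, or 2.9 to 11.4 percentage points. Section 1 expects chronic postsurgical pain in 10 to 20% of children having surgery: 0.10 × 35 = 3.5 to 0.20 × 35 = 7 cases per group. One to four unknown outcomes are not negligible beside that.

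**The case against.** **The limit in section 13.5 may mean the planned six months.** Sections 8.1 and 9.1 describe participation as lasting six months, and section 13.5 also says that follow-up information on an event goes to the sponsor and IRB. That reading is possible and may be what was intended. But the text refers to the patient's own participation, which section 9.5.2 says can end early, and forwarding information presupposes that it is still being collected. The consent form is not among the documents reviewed, so any terms there cannot be seen.

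**The affected group is narrow.** This stands. The list in section 9.5.2 is permissive and its bullet concerns an event that prevents the patient from continuing, not mere intolerance of the drug. Section 13.4 says most effects are mild and diminish, and a history of depression is an exclusion. Clinical care would continue in any case.

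**Patients who stop the drug are already kept.** Largely right. A reader might infer that the drug can be stopped for a side effect, with the patient retained, only after un-blinding. The documents do not support that: section 10 retains patients who miss doses without opening the code, and nothing forbids withholding a dose. Nor does the non-compliance example in section 9.5.2 contradict section 10, since it is only permissive.

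**The mixed model handles missing scores.** Partly. Section 16.4 chose it for that flexibility, and it uses whatever scores were collected. It does not serve the chi-square comparison, for which no missing-data method is stated; that gap applies to dropout for any reason.

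**Conclusion.** The point holds as a gap in the follow-up rule. As written, an unresolved adverse event that causes exit need not be followed to its outcome, and the patient's later pain outcomes are lost when they might have been collected.

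The main cost is to the safety record. The effect on the primary mean is likely small, power is not threatened, and the effect on the chronic-pain rate depends on an exit rate that the documents do not give. The sizes rest on the assumed 1 to 4 exits per 35 and the assumed 1 to 2 point difference.

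Three stronger readings should be resisted:

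- Both primary scores are not always lost. That is so only for exit before week 6.
- The frequencies in section 13.4 do not measure the problem. At 1 to 10%, depression or sleep disorder would each affect 0.7 to 7 of 2 × 35 = 70 clonidine patients, but that counts any such event, not those that end participation unresolved.
- No bias for or against clonidine can be inferred, because nothing shows which arm would lose more patients or how their pain would differ.

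**What to change.** - **Section 13.5:** follow every adverse event until it is resolved or stable, including after study drug is stopped or the patient leaves the study, unless consent is withdrawn.
- **Section 9.5.2:** state that during the dosing period an adverse event ends study drug rather than participation where the patient is willing to stay. A patient who cannot attend is asked by phone for the 6-week and 6-month pain rating and, at 6 months, chronic-pain status.
- **Section 13.7 (optional):** say that the request to remain also applies when oral drug is stopped for an event with the code sealed. This is only a clarification, given section 10.

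The cost is a few sentences of protocol text and at most two phone calls per affected patient. Weekly calls are already planned and, per section 17, study visits coincide with standard-of-care visits, so no new visit or procedure is needed.
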